10.1 Statistical and Analytical Plans (SAP)

As the study is a pilot randomized trial, the results are expected to inform the overall protocol design for a larger effectiveness evaluation, including the statistical analysis plan. Our overall strategy will be to estimate the primary and secondary outcomes for those randomized to HLA, along with the contemporary cohort randomized to vaginal estrogen. Formal comparisons between randomized groups are not of focus, but we will estimate treatment effects along with measures of variability in these measures (95% CI).

10.2 Statistical Hypotheses

We expect no clinically meaningful differences in baseline characteristics or baseline assessment of outcomes between those randomized to HLA or to vaginal estrogen, however this is possible given the limited pilot trial sample size. These differences will be assessed and considered in the evaluation of outcomes for primary and secondary endpoints.

We expect a clinically meaningful improvement in the change measured at 12 weeks (comparison of VSQ at 12 weeks, adjusted for baseline) in VSQ in the HLA group, and expect this to be greater as compared to those randomized to vaginal estrogen. Similarly, we expect to observe clinically meaningful improvements in the HLA group at 12 weeks, beyond those observed in those randomized to the vaginal estrogen cohort. These include VSI, FSFI, VAS for dyspareunia, itching, and dryness, vaginal pH, and presence of rugal folds.

CONFIDENTIAL

This material is the property of the NYU School of Medicine and Langone Medical Center. Do not disclose or use except as authorized in writing by the study sponsor
Interventional Template Version: 11 January 2019

These estimates will provide estimates for establishing effectiveness in future trials.

10.3 Analysis Datasets

The analysis dataset will include the intent to treat cohort, to include all those randomized to treatment, as well as a per protocol set to include who used either the control or investigational product for at least 12 weeks.

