6.1.5 Dosing and Administration

The study agent, Revaree, has only one dose. As per the manufacturer, the suppository should be placed in the vagina at bed time. It should be removed from the packaging before insertion, inserted into the vagina while laying down with knees bent, and then pushed further into the vagina gently, as far as tolerated. It should be placed twice weekly.

The control agent, Estrace, is dosed by the amount of cream applied to the vagina. The patient will need to attach the applicator to the tube and squeeze the cream into the calibrated applicator accordingly before application at bed time. The dosing will be 100mcg of estradiol (1g of cream) inserted into the vagina twice a week. This dosing is consistent with the manufacturer recommended maintenance dosing for Estrace and it mimics the usage pattern of the other study agent, HLA. Additionally, a study of a similar vaginal cream, Premarin, showed that twice weekly dosing was as efficacious and safe as using the cream daily for 21 days and 7 days off for GSM symptoms (22).

CONFIDENTIAL

This material is the property of the NYU School of Medicine and Langone Medical Center. Do not disclose or use except as authorized in writing by the study sponsor
Interventional Template Version: 11 January 2019

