6.1.9 Duration of Therapy

The duration of therapy will be 12 weeks. This is based on evidence that vaginal estrogen therapy can take up to six weeks to offer symptomatic relief in some patients (16). Additionally, with four weeks of usage, vaginal administration of HLA has shown to have significant impact on GSM symptoms.

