6.2 Study Agent Accountability Procedures

NYU Investigational pharmacy will be used to ensure the drug and device are stored and dispensed in a regulated manner through the faculty group practice study site. Unused product will be returned to JDS Therapeutics ([name]). Both medications will be stored at the office in a locked cabinet. There will be no additional interventions.

Regular study drug reconciliation will be performed to document drug assigned, drug consumed, and drug remaining. This reconciliation will be logged on the drug reconciliation form, and signed and dated by the study team.

7 Study Procedures and Schedule

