10.4.4 Adherence and Retention Analyses

Due to the nature of this study, study agent usage will be assessed solely by patient self-report. Participation and study retention will be assessed by a ratio of those who participated divided by the total starting cohort for that study arm. Those that discontinue and provide a reason for discontinuation will be categorized and the information will be presented in a table.

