10.5 Sample Size

This study would be the first US-based randomized trial investigating HLA's usage for GSM treatment, to the authors' best knowledge. Thus, the sample size of 60 has been chosen to pilot the presented protocol, to assess feasibility and acceptability in quality of life for HLAs and to gather preliminary effectiveness for planning a larger effectiveness trial. The authors acknowledge the limitations of having enrolling 60 individuals, including generalizability. However in this initial stage of study implementation and design, expect this number to provide sufficient information.

No study to date has used the VSQ to assess the impact of treatment modalities for GSM, so there is no historical data to provide an assumed mean score. However, with 30 individuals randomized to each study treatment, we expect to have at least 80% probability of achieving a 95% confidence interval (CI) width of 1.7, assuming a standard deviation in the VLM of 2. With fewer individuals at any timepoint, the width of the CI will increase.

The assumed drop-out, withdrawal, cross-over and missing data rate is assumed to be 33%, which explains the enrollment goal of 60 to allow for 40 evaluable patients. This is a conservative estimate because the missing data rates in RCT's from four major journals has shown to be 20% or greater in about 18% of trials, which was also seen in quality-of-life studies (26, 27). We will monitor reasons for drop out and withdrawal of treatment to improve study adherence and follow up.

All participants will be included in the intent to treat analyses, and those participants who use the study intervention for at least 12 weeks will be included in the per-protocol analysis.

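### The per-protocol set is defined by 12 weeks of use with no minimum share of planned applications, and adherence rests on self-report alone although product reconciliation is already required

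*Combined protocol and SAP*

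**What the plan says.** **Per-protocol set.** Section 10.3 names an intent-to-treat cohort and "a per protocol set to include who used either the control or investigational product for at least 12 weeks". Section 10.5 repeats the rule: "those participants who use the study intervention for at least 12 weeks will be included in the per-protocol analysis". Neither section sets a minimum number or share of applications, and neither uses the word assigned.

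**Planned use.** Section 6.1.5 says of the insert "It should be placed twice weekly", and the cream is to be "inserted into the vagina twice a week". Section 6.1.9 adds: "The duration of therapy will be 12 weeks".

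**Measuring use.** Section 10.4.4 states that "study agent usage will be assessed solely by patient self-report". The dosing diary in 6.1.10 and the compliance report in 7.1.1 also come from the participant. Section 6.2, on accountability, states: "Regular study drug reconciliation will be performed to document drug assigned, drug consumed, and drug remaining". It has this logged and signed, but does not say that it is done per participant.

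**Role of compliance.** It is a secondary endpoint in the Protocol Summary, where it is to be described by treatment group, and part of the secondary objective in 3.2.

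**Visit 2 timing.** Section 7.2.4 allows 3 to 5 days either side of week 12. Section 20 allows one week.

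**Changes to treatment.** Section 4.1 rules out protocol changes to either medication. Section 6.1.8 allows the cream dose to be reduced if side effects occur.

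**The concern.** A per-protocol estimate is meant to describe women who used the treatment broadly as planned. A rule based on duration alone shows that a woman was still using the product at 12 weeks, not how much of it she used. Someone who applied it rarely but never formally stopped counts the same as someone who made every application.

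The measurement rule adds to this. Women know which product they received, and Section 10.6.1 accepts that lack of blinding may bias what patients report about symptoms. Reports of adherence could be affected in the same way. Restricting the adherence analysis to self-report shuts out the only record in the plan that need not depend on it.

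At stake is what the pilot passes on. Section 10.1 says its results are to inform the protocol and analysis plan of a larger trial, and adherence is one of the things that trial will need to know. If the threshold and data source are settled after the data are seen, in an open-label study, membership of the per-protocol set becomes a choice made with outcomes in view.

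**Working it through.** **1. Planned applications.** Inputs: twice weekly (6.1.5) and 12 weeks (6.1.9, Protocol Summary).

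2 per week × 12 weeks = 24.

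**2. What the duration rule admits.** The two women below are illustrations, not data.

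- 6 applications spread over 12 weeks: 6/24 = 25%, so 18 missed (75%).
- 12 applications spread over 12 weeks: 12/24 = 50%, so 12 missed (50%).

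Both qualify under 10.3 and 10.5, and no lower limit is stated.

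**3. What the duration rule excludes.** Week 12 is day 84.

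- Section 20: 84 − 7 = day 77 is the earliest in-window visit.
- Section 7.2.4, wider limit: 84 − 5 = day 79.
- Section 7.2.4, narrower limit: 84 − 3 = day 81.

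A woman seen on any of these days is on schedule but has under 12 weeks of use at her visit. Read to the letter, she is outside the per-protocol set. Sections 5.5 and 7.2.5 suggest that 12 weeks means the completed course, so this is a wording gap and not a design intention.

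**4. A workable denominator.** Therapy ends at 12 weeks, so the count of planned applications must stop at 24:

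planned = 2 × min(day of Visit 2, 84) / 7

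- Day 77: 2 × 77/7 = 22.
- Day 79: 2 × 79/7 = 22.6.
- Day 84 or later: 2 × 84/7 = 24.

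A percentage is better than a fixed count because of the early visits: 20 applications are 20/22 = 91% at day 77 and 20/24 = 83% at day 84 or later. With the cap, a woman who made all 24 scores 100% however late she is seen.

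**5. Assigned product.** Section 10.5 says: "The assumed drop-out, withdrawal, cross-over and missing data rate is assumed to be 33" per cent. That rate reproduces the enrollment target: 40/(1 − 0.33) = 59.7, rounded up to 60; and 60 × 0.67 = 40.2. Cross-over therefore sits among the losses that take 60 enrolled to 40 evaluable. This fits a reading in which women who switch product are not counted as treated per plan, although 10.3 does not say so.

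**6. Sources of adherence data.** Section 10.4.4 admits self-report only, and the diary and Visit 2 report are both of that kind. The reconciliation in 6.2 is not linked anywhere to adherence or to per-protocol membership. Visit 2 has a place to record it: an adherence record in 7.2.4 and a compliance check in Section 20. Neither lists product return or counting.

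**The case against.** The strongest reply is that this is an estimation pilot. Formal comparisons are not its focus (10.1), the mixed model in 10.4 uses all participants, and the intent-to-treat set is analyzed alongside. Twelve weeks of use is itself a criterion, and any percentage threshold is a matter of choice that would shrink an already small set. The dated diary could supply a percentage without new procedures. All of this stands, and it limits the point to the per-protocol and compliance results. It does not remove the need to say in advance what the set means.

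Three stronger readings are tempting, but the documents do not support them.

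- *The per-protocol set is meant to admit women who used the other arm's product.* A reader might infer this from the phrase covering either product. It more naturally means that the rule applies to both arms, and 10.5 counts cross-over as loss. The missing word is probably loose drafting.
- *Sections 6.2 and 10.4.4 contradict each other.* They do not. Reconciliation can serve accountability only, and 6.2 does not promise a count per participant. The weakness is an unused record.
- *Applications go on accruing until a late Visit 2.* Nothing says so. Therapy is 12 weeks, so the planned total stays at 24.

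**Conclusion.** The point holds in a limited form. The per-protocol definition measures persistence and sets no floor on use of the 24 planned applications. Taken literally, it drops women seen on schedule up to 7 days before day 84. Adherence, a secondary endpoint, is to rest on unblinded self-report while a reconciliation already called for is left out.

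How many women this would affect cannot be derived from the documents, so no figure for bias or lost precision is given; the 25% and 50% cases only show what the wording permits. A reader might also infer that the main results are compromised. They are not: the intent-to-treat analysis, the sample size and the decision rules do not depend on this definition. The conclusion assumes twice-weekly use over exactly 12 weeks and that the reconciliation can be recorded per participant, which 6.2 leaves open. The change is worth making because it is cheap and must be fixed before outcomes are known.

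**What to change.** 1. **Section 10.4.4.** Replace the self-report-only rule with diary and self-report plus the 6.2 reconciliation. Record the reconciliation per participant at the existing Visit 2 compliance check, report both sources by arm, and state which prevails when they disagree. *Cost:* Visit 2 may need a product-return line. Amounts remaining are less exact for cream than for inserts, so precision will differ by arm, which is why both sources should be shown.

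2. **Sections 10.3 and 10.5.** Say assigned product. Require a minimum percentage, chosen and justified by the team in advance, of the applications planned up to the earlier of day 84 and the woman's own Visit 2, never more than 24. State that an in-window visit before day 84 counts as completing the course. *Cost:* a smaller per-protocol set than the current wording gives.

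3. **Consistency.** Reconcile the Visit 2 windows in 7.2.4 and Section 20. Reconcile 4.1 with 6.1.8, and state how a woman whose cream dose was changed is classified for the per-protocol set. This affects the cream arm only: judged by the amount left, she could look non-adherent although she made every application. *Cost:* wording. Which window, and which statement on dose changes, should stand is for the study team to decide.

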10.4 Description of Statistical Methods

Baseline (pre-randomization) participant demographics and clinical characteristics will be summarized through descriptive statistics overall, and by randomized group. Clinical characteristics will include past HRT use, uterus present or not, and components of their medical and gynecologic history. Details of each outcome measure is provided below. Analysis of the primary and secondary measures will include summarizing each by the mean and standard deviation at baseline and all measured time points, including at the primary outcome time of 12 weeks. For continuous measures, a linear mixed effects regression model will estimate the mean outcome at 12 weeks, both unadjusted and adjusted for baseline measurement. No further adjustment for participant characteristics is expected given the limited trial size. The linear mixed effects regression model will allow all participants to be included in analysis, regardless of completion of study follow up at 12 weeks, under the assumption of this assessment being missing at random.

Missing outcome data will be summarized by participant characteristics to understand how to better retain individuals in treatment.

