4.2 Study Endpoints

4.2.1 Primary Study Endpoints

The primary endpoint will be the change in the VSQ score, between the baseline visit and 12 week follow-up.

The VSQ is a 21-question survey developed in 2012 that specifically asks about GSM symptoms, their emotional impact, sexual impact, and life impact. Among 120 post-menopausal women, this questionnaire was found to have reliability and internal consistency (15). Most importantly, in the absence of a gold standard instrument to assess the quality of life impact of

CONFIDENTIAL

This material is the property of the NYU School of Medicine and Langone Medical Center. Do not disclose or use except as authorized in writing by the study sponsor
Interventional Template Version: 11 January 2019

GSM, this questionnaire is critical. It is more nuanced and disease-specific than VAS scoring, and thus far, an underutilized tool to understand the significant psychological impact of this disease. Because GSM is a symptom-driven disease and patients will likely adhere to a treatment plan if they perceive symptomatic improvement, this study's primary endpoint of treatment success will be measured by improvement in VSQ scoring.

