5.5 Duration of Study Participation

There is no pre-screening to visit one. After visit one, the patient will have a follow-up visit approximately 12 weeks later. There is no follow up required after the 12 week visit. Thus, the duration of study participation is 12 weeks.

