5.6 Total Number of Participants and Sites

Recruitment will end when approximately 60 participants are enrolled at this single site at NYUMC. It is expected that approximately 60 participants will need to be enrolled in order to retain 40 evaluable participants at 12 weeks of follow up (an overall 33% drop out rate).

CONFIDENTIAL

This material is the property of the NYU School of Medicine and Langone Medical Center. Do not disclose or use except as authorized in writing by the study sponsor
Interventional Template Version: 11 January 2019

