5.7.2 Handling of Participant Withdrawals or Termination

Patients who withdraw or terminate participation in this study will be called and a follow-up office visit will be set up at 12 weeks regardless of their participation. If the patient refuses to come in, a phone call will be made to discuss adverse events or unanticipated problems over the phone. If a patient is lost to follow-up, two phone calls to the patient and subsequently two phone calls to next-of-kin will be made in an attempt to reach the patient. There is low concern for long-term and short-term safety with either study agent, particularly for the duration of eight weeks only.

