7.2.5 Withdrawal/Early Termination Visit

If 12 weeks of study agent usage:

- Record AE as reported by participant or observed by investigator
- Record participant's adherence to treatment regimen
- Obtain GSM symptom history, and record VAS scores for dyspareunia, itching, and dryness
- Record vital signs, results of physical exam including pelvic
- Collect pelvic samples for vaginal pH and vaginal tissue scraping for vaginal maturation index
- Have patient fill out VSQ
- Discuss the obvious, preliminary changes in their symptoms, if any exist
- Provide contact information for [name] to communicate any AE or side-effect experienced after the end of the study if patient believes it is related to the study

If <12 weeks of study agent usage:

- Record AE as reported by participant or observed by investigator
- Record participant's adherence to treatment regimen
- Record vital signs, results of physical exam including pelvic
- Provide contact information for [name] to communicate any AE or side-effect experienced after the end of the study if patient believes it is related to the study

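### Section 10.4 says its mixed model uses all participants, but as worded it reads as a completers' ANCOVA, so HLA-arm estimates can be biased if dropout depends on baseline

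*Combined protocol and SAP*

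**What the plan says.** The primary endpoint is a change score. Section 4.2.1: "The primary endpoint will be the change in the VSQ score, between the baseline visit and 12 week follow-up". For the analysis, section 10.4 says that "a linear mixed effects regression model will estimate the mean outcome at 12 weeks, both unadjusted and adjusted for baseline measurement", and section 10.2 describes the VSQ analysis as a "comparison of VSQ at 12 weeks, adjusted for baseline". Section 10.4 then claims that the model "will allow all participants to be included in analysis, regardless of completion of study follow up at 12 weeks", under missing at random.

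There is one post-baseline assessment. Section 5.5: "After visit one, the patient will have a follow-up visit approximately 12 weeks later". The Schedule of Events (section 20) lists the VSQ at Day 0 and week 12 only.

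On expected loss, section 5.6 plans 60 enrolled to keep 40 evaluable and calls this "an overall 33% drop out rate". Section 10.5 uses the same 33% but counts withdrawal, cross-over and missing data within it. Section 5.7.2 says that for women who withdraw "a follow-up office visit will be set up at 12 weeks regardless of their participation". In section 7.2.5, the list under "If <12 weeks of study agent usage" contains no VSQ.

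The plan does not state the response vector, the random effects or covariance structure, or the baseline value at which adjusted means are evaluated. It plans no imputation.

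**The concern.** A mixed model keeps a woman with a missing week-12 score only if some other measurement of hers is a response. With one follow-up visit, that measurement can only be baseline. The wording of 10.2 and 10.4 instead makes week 12 the outcome and baseline the adjustment. A programmer following it could fit a completers' ANCOVA while the report states that all randomised women were analysed.

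What is at stake is mainly the arm-level estimates. The Protocol Summary and section 10.1 put the focus on outcomes in the HLA group rather than on formal comparison, and section 10.2 intends these estimates for planning later trials. Missing at random, the plan's own assumption, allows dropout to depend on baseline severity. Completers' means then describe the women who stayed, not those randomised.

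**Working it through.** **The plan's own figure.** 40 / (1 − 0.33) = 59.7, rounded up to 60; forward, 60 × 0.67 = 40.2. The 60 and 40 reproduce, and 60 − 40 = 20 women without evaluable week-12 data.

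**Who enters the model.** In a simulated trial of 60 women with 45 week-12 scores, a mixed model with week 12 as response and baseline as covariate used 45 women and gave the same coefficients as ordinary ANCOVA. With baseline and week 12 both as responses, all 60 women contributed (60 + 45 = 105 rows).

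**Inputs for the size of the bias**
- Loss: one third (20 of 60), from sections 5.6 and 10.5.
- SD 2: section 10.5 gives it for a measure it calls the VLM, which is not in the abbreviation list. Using it for the VSQ at both visits is an assumption.
- Baseline to week-12 correlation r = 0.3, 0.5, 0.7: assumption.
- Dropout log-odds of 0.5 or 1.0 per baseline SD, with more symptomatic women leaving: assumption.

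**Formulas.** Take baseline as normal and the probability of a missing score as logistic in baseline, with the intercept set to give the stated loss. Let s be the completers' mean baseline minus the all-randomised mean.
- Bias in the completers' week-12 level = r × s.
- Bias in the completers' mean change (week 12 minus baseline) = (r − 1) × s.

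Example at log-odds 1.0 and r = 0.5: s = −0.558, level bias 0.5 × (−0.558) = −0.279, change bias (−0.5) × (−0.558) = +0.279.

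| Loss | Log-odds | s | Level bias, r = 0.3 / 0.5 / 0.7 | Change bias, r = 0.3 / 0.5 / 0.7 |
|---|---|---|---|---|
| 1/3 | 0.5 | −0.316 | −0.10 / −0.16 / −0.22 | +0.22 / +0.16 / +0.10 |
| 1/3 | 1.0 | −0.558 | −0.17 / −0.28 / −0.39 | +0.39 / +0.28 / +0.17 |
| 20% | 0.5 | −0.192 | −0.06 / −0.10 / −0.13 | +0.13 / +0.10 / +0.06 |
| 20% | 1.0 | −0.347 | −0.10 / −0.17 / −0.24 | +0.24 / +0.17 / +0.10 |

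A higher VSQ is worse. If more symptomatic women leave, the week-12 level is too low and the improvement looks too small; if less symptomatic women leave, both signs reverse. If dropout is unrelated to baseline, s = 0 and so is the bias.

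**Against precision** (simulation, 30 per arm, one-third loss):
- Unadjusted HLA level: 95% CI half-width 0.89 to 0.93, bias 10% to 44% of it, coverage 87% to 95%.
- Mean change: half-width 0.71 to 1.09, bias 13% to 37% of it, coverage 89% to 94%.

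**Adjusted HLA mean** (r = 0.5, log-odds 1.0):
- At the completers' baseline it is off by −0.29 when both arms lose women in the same way, −0.14 when only HLA dropout depends on baseline, and about 0 when the arms go in opposite directions.
- At the all-randomised baseline it is off by about 0 in all three cases.

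**Arm difference** (same setting):
- Baseline-adjusted: bias 0.00 to 0.01 in all three cases.
- Unadjusted: about 0 with the same pattern in both arms; −0.28 − 0 = −0.28 if only HLA dropout depends on baseline; −0.28 − 0.28 = −0.56 if the arms go in opposite directions.

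**The two remedies agree.** On three simulated data sets, maximum likelihood for the two-response model with a common baseline mean matched ANCOVA at the all-randomised baseline to three decimals. In one, both gave an HLA mean of 6.338, against 6.069 at the completers' baseline.

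**The case against.** The strongest reply is that the plan names a mixed model and says it keeps everyone under missing at random. With one row per woman, a subject effect cannot be separated from residual error, so only a two-response model fits both statements. This stands in part: a reader might infer that the plan is proven to exclude women, and the documents do not show that. They describe a week-12 outcome adjusted for baseline and leave the response vector unstated. Nor does the two-response reading settle the text, because the planned baseline-adjusted version would put the same measurement on both sides of the model.

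A reader might also take 20 as a firm count or a ceiling. It is neither. It is an assumed loss that includes cross-overs, who may have a week-12 score, and the plan seeks a 12-week visit after withdrawal.

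The bias is also small on a 0 to 21 scale and rests on assumed inputs. That is fair, and it limits the weight of the point. Finally, in an open-label trial dropout may follow response rather than baseline. If it depends on the week-12 score itself (log-odds 0.5 to 1.0), a level bias of 0.17 to 0.52 points remains after the fix. The fix is therefore only partial protection.

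**Conclusion.** The inclusion statement in 10.4 does not hold for the model that its wording most naturally describes, and the model for which it would hold is not specified. The defect is an incomplete and internally inconsistent specification; exclusion of women is likely rather than proven.

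If the completers' model is fitted and dropout depends on baseline, the unadjusted HLA mean or change, or the adjusted HLA mean at the completers' baseline, would be off by roughly 0.1 to 0.4 VSQ points at one-third loss. For the adjusted mean, this range applies when both arms lose women in a similar way. The size rests on SD 2 at both visits, correlation 0.3 to 0.7 and dropout log-odds 0.5 to 1.0 per baseline SD.

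It would be wrong to infer that the treatment comparison as a whole is invalid. The baseline-adjusted arm difference is essentially unaffected if dropout depends only on baseline and the linear model holds. It would equally be wrong to clear every arm difference: the unadjusted one, if reported, would be off by about 0.3 to 0.6 points at correlation 0.5 and log-odds 1.0 when dropout patterns differ by arm. The plan should be corrected, but the point does not threaten the trial.

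**What to change.** In section 10.4, specify one of two equivalent main analyses, in place of the unadjusted completer estimate:

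1. Baseline and week-12 VSQ both as responses, with unstructured 2 × 2 covariance, a common baseline mean, visit and arm-by-week-12 terms, and no baseline covariate.
2. ANCOVA on week 12, with arm means evaluated at the mean baseline of all randomised women. The CI must allow for estimating that mean: the default interval treats it as fixed, and for the mean at the completers' baseline it covered only 90% to 94% even with dropout unrelated to baseline.

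Report each arm's week-12 mean, its change from baseline and the arm difference, with 95% CIs. Reword the inclusion sentence to say that women without week 12 contribute baseline data only. State that the analysis removes bias only under missing at random given baseline, and that only the baseline-adjusted arm difference is essentially unchanged by it.

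The cost is one paragraph of SAP text and standard software, with no new data or visits.
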